**4.1.5 Safety analysis set (SAF)**

All participants in the Exposed Set who provide any evaluable post-vaccination reactogenicity and/or safety data (including VS and ECG data).

Should there be an error in administration where the actual study vaccine that the participant received was different than the one to which he/she was assigned, the Safety Analysis Set will be analyzed according to the vaccine actually received.

Note: in case of incorrect vaccine received, the actual vaccine received will be provided after database lock by unblinded monitor.

**4.1.6 Historical control set (ARCT-154-J01)**

All participants from study ARCT-154-J01 who received a booster with ARCT-154 vaccine, provided evaluable pre- and post-vaccination blood samples, and did not have SARS-CoV-2 infection and protocol deviations that impact on immunogenicity assessment. These participants were included in the per-protocol set 1 for the primary immunogenicity analysis.

## 5 SUMMARY OF STUDY DATA

### 5.1 Participant disposition and analysis populations

Participant disposition and analysis population analysis will be based on the Enrolled Set. Participant disposition and analysis populations will be summarized descriptively as described in section 3.1 (categorical descriptive analysis).

#### 5.1.1 Participant Disposition

Participant disposition will include the number of participants who complete the full course of study treatment, participants who did not complete treatment, reason treatment was not completed, participants who completed the study, participants withdrawn from the study, as well as the primary reason for early discontinuation. Participant disposition will be summarized descriptively overall and by group.

#### 5.1.2 Analysis Populations

The number of participants included in each analysis set will be summarized descriptively.

Reasons for exclusions from mITT, PP Day 29, and PP Day 181, including corresponding exclusionary PDs for PP Day 29 and PP Day 181, will be summarized accordingly.

In addition, the inclusion/exclusion of each participant into/from each of the defined analysis sets will be presented in the by-participant data listings.

### 5.2 Protocol deviations

Reportable protocol deviations (PD), including Exclusionary PDs and Other Reportable (non-Exclusionary) PDs, will be summarized for Day 1 to Day 57 and for Day 1 to End of Study (EOS) by treatment group for the ITT analysis set.

For first final analysis, Exclusionary PDs for PP (Day 29) and Other Reportable PDs up to the date of data lock for this analysis will be reported. For second final analysis, all Exclusionary PDs and Other Reportable PDs for Day 1 to End of Study will be reported.

All Reportable protocol deviations will be presented for each participant in by-participant data listings (for Day 1 to Day 57 and Day 1 to EOS).

Protocol deviations will be reviewed by medical monitors and categorized as noted in the Project Specific Protocol Deviation Specifications, including assessment of severity (major or minor).

Prior to database lock protocol deviations and analysis sets will be reviewed and confirmed to decide which subjects and/or subject data will be excluded from certain analyses. Decisions regarding exclusion of subjects and/or data from analyses will be documented and approved prior to database lock.

### 5.3 Demographic and baseline information

Demographic and baseline information analysis will be presented for the ITT and PP analysis sets.

Demographic and baseline information will be summarized descriptively overall and by treatment group, as described in section 3.1.

#### Demographics

The following demographic and baseline parameters will be analyzed:

##### Continuous descriptive analysis:

Age (years)

Height (cm)

Weight (kg)

BMI (kg/m^2)

Categorical descriptive analysis:

Age Category (18-64 years, 65+ years)

Sex

Race

Ethnicity

Country (derived by using the first digit of the site number)

Similarly, the available demographic and baseline parameters will be summarized for ARCT-154 recipients (study ARCT-154-J01) too.

For study ARCT-2303-01 participants, age collected on CRF is used for the analysis, while age at the time of first vaccination is considered for study ARCT-154-J01 participants.

#### **5.4 Risk Factors**

Risk factors for severe COVID-19 at enrolment will be summarized descriptively overall and by study group for the ITT analysis set, as described in section 3.1.

#### **5.5 COVID Vaccination History**

COVID vaccination history data will be summarized by treatment groups for the ITT analysis set:

- Subject received at least 3 doses of vaccine (last dose  $\geq$ 5 months prior to enrolment) (Yes, No)
- Number of COVID-19 vaccine doses
- Name of licensed COVID-19 vaccine
- Primary series based on first two doses (derived)
- Vaccine composition of last dose
- Name of last vaccine/booster vaccine

COVID vaccination history responses will be presented in the by-participant data listings. A listing comparing stratification factors as per CRF v. IRT will be generated.

#### **5.6 Treatment Exposure**

All study vaccine administration information on Day 1 and Day 29, including study vaccine administered (Yes/No), date and time of administration, location (left arm/right arm) will be presented in the by-participant data listings. Information on diary dispensation, activation and training will also be included in the same listings.

Number and percentage of participants who received each vaccine will be summarized by study group for the Safety analysis set, as described in section 3.1. Contraindications for the Second Vaccination will be presented in the by-participant data listings. Vaccination errors (or mis-dose) will be listed.

#### **5.7 Prior and concomitant medications**

Prior and concomitant medications for Day 1 to Day 57, as well as concomitant medications from Day 1 to EOS will be summarized for the Safety analysis set by Anatomical Therapeutic Chemical (ATC) class Level 2 and PT as noted in section 3.1 (categorical descriptive analysis). Participant who used the same medication on multiple occasions will only be counted once in the specific category. ATC Level 2 and PTs will be sorted alphabetically. In addition to the summaries by the coded terms, the number of participants who used at least one concomitant medication during the study will be presented.

Prior and Concomitant medications will be presented in the by-participant data listings.

### **5.8 Medical history**

Medical history will be coded using MedDRA® and will be summarized by treatment groups, SOC and PT, for the Safety analysis set.

Medical history data will be presented in the by-participant data listings.

### **5.9 Surgical and Medical Procedure**

Surgical and medical procedure as collected on the "Surgical and Medical Procedures" CRF page will be presented in the by-participant data listings.

## **6 EFFICACY**

No efficacy analysis is planned for this study.

## 7 SAFETY

Safety endpoints will be analyzed using the Safety analysis set and will be summarized descriptively as described in section 3.1.

### 7.1 Solicited Adverse Events

Information on Solicited Adverse Events will be summarized descriptively by treatment group, as described in section 3.1.

- Solicited local reactions and systemic AEs will be recorded daily within 7 days after each study vaccination:
  - Local reactions: pain, erythema and swelling at the injection site.
  - Systemic AEs: fatigue, headache, myalgia, arthralgia, nausea, dizziness, chills, and fever.

Severity grading for these AEs is presented in Table 1. Severity will be categorized programmatically as Mild, Moderate and Severe based on data collected on the eDiary and applying the definition provided in Table 1.

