- Hemagglutination Inhibition (HI) assay against influenza vaccine strains. In case of lack of agglutination for a specific strain using HI assay, immunogenicity for that strain will be assessed as measured by microneutralization (MN) assay;
- MN titers against influenza vaccine strains.

The results of HI and MN will be analyzed as:

- Geometric mean titer (GMT) on Days 1 and 29;
- Geometric mean-fold ratio (GMFR) as increases of the post-vaccination titer over the pre-vaccination titer;
- SCR on Day 29 as the percentage of participants in a group with either:
 - A pre-vaccination titer below the LLOQ for the respective assay and a post-vaccination titer $\geq 4 \times \text{LLOQ}$; or
 - A pre-vaccination titer $\geq \text{LLOQ}$ and a ≥ 4 -fold increase in post-vaccination titer.
- Proportion of participants with HI titer $\geq 1:10, 1:20, 1:40, 1:80, 1:160$ and $1:320$ on Days 1 and 29;
- Proportion of participants with MN titer $\geq 1:10, 1:20, 1:40, 1:80, 1:160$ and $1:320$ on Days 1 and 29.

CONFIDENTIAL

May not be used, divulged, published or otherwise disclosed without written consent of Arcturus Therapeutics, Inc.

Safety assessments:

- All participants will be monitored for 30 minutes after each study injection for any immediate post-vaccination adverse events (AEs) with appropriate medical treatment readily available in case it is needed.
- Solicited local reactions and systemic AEs will be recorded daily within 7 days after each study vaccination:
 - Local reactions: pain, erythema and swelling at the injection site.
 - Systemic AEs: fatigue, headache, myalgia, arthralgia, nausea, dizziness, chills, and fever.

On Day 1, when ARCT-2303 will be co-administered with the influenza vaccine, participants will be instructed to record local reactogenicity for both arms separately.

Specifically, participants in:

Group 1a and 1b will receive: ARCT-2303 on the left arm and influenza vaccine on the right arm

Group 2a and 2b will receive: ARCT-2303 on the left arm and placebo on the right arm

Group 3a and 3b will receive: placebo on the left arm and influenza vaccine on the right arm

- Any unsolicited AEs will be collected within 28 days after each study vaccination (from Day 1 to Day 29 and from Day 29 to Day 57).

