8.12.3 Vaccination and Post-vaccination Procedures (Day 1 and Day 29)

Perform randomization ([Section 8.8](#)) at Visit 1 (Day 1).

After confirming eligibility ([Section 8.7](#)) at Visit 1 (Day 1) and at subsequent vaccination visit (Day 29), ensure that the participant does not meet criteria for delay or discontinuation ([Section 5.3](#)).

Perform vaccination ([Section 8.9](#)).

CONFIDENTIAL

The following post-vaccination procedures will be performed at Visit 1 (Day 1) and Visit 2 (Day 29):

- Participants will be observed for 30 minutes after vaccination in case of any adverse reaction. Any AEs reported within 30 minutes after vaccination will be recorded in the eCRF.
- After study vaccine administration, vital signs will be measured (BP, RR, body temperature, and heart rate) and vital sign measurement should be repeated if clinically indicated.

Careful training of the participant (or the individual who will be performing the measurements) on how to measure local reactions and body temperature, how to complete and how often to complete the eDiary will occur at Visit 1.

At Day 1, when two study vaccines will be co-administered, participant will be instructed to record local reactogenicity for both arms separately.

Specifically, participants in:

Groups 1a and 1b will receive: ARCT-2303 on the left arm and influenza vaccine on the right arm,

Groups 2a and 2b will receive: ARCT-2303 on the left arm and placebo on the right arm,

Groups 3a and 3b will receive: placebo on the left arm and influenza vaccine on the right arm.

At Day 29, vaccine administration will be done in the non-dominant arm.

eDiary instructions must include the following:

- The participant must understand that timely completion of the eDiary on a daily basis is a critical component to study participation.
- The participant should be instructed on how to complete the eDiary and how to make corrections to erroneous entries.
- Starting on the day of vaccination, the participant will check approximately 6 hours post-vaccination (minimum of 4 hours post-vaccination) for specific types of reactions at the injection site (solicited local adverse reactions), any specific generalized symptoms (solicited systemic AEs), body temperature (preferably axillary), any other symptoms or change in the participant's health status, and any medications taken.

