**Table 1 Severity Grading for Solicited Local Reactions and Systemic Adverse Events**

	Mild	Moderate	Severe
Pain	No interference with daily activities	Interferes with daily activities	Prevents daily activity
Erythema	25-50 mm	51-100 mm	> 100 mm
Swelling	25-50 mm	51-100 mm	> 100 mm
Fatigue	No interference with daily activities	Interferes with daily activities	Prevents daily activity
Headache	No interference with daily activities	Interferes with daily activities	Prevents daily activity
Myalgia	No interference with daily activities	Interferes with daily activities	Prevents daily activity
Arthralgia	No interference with daily activities	Interferes with daily activities	Prevents daily activity
Nausea	No interference with daily activities	Interferes with daily activities	Prevents daily activity
Dizziness	No interference with daily activities	Interferes with daily activities	Prevents daily activity
Chills	No interference with daily activities	Interferes with daily activities	Prevents daily activity
Fever (°C)	38.0-38.4	38.5-38.9	≥39.0

Note: Based on Food and Drug Administration (FDA) Guidance Document: Toxicity Grading Scale for Healthy Adult and Adolescent Volunteers Enrolled in Preventive Vaccine Clinical Trials.

The following parameters will be summarized by treatment group using descriptive statistics:

- Time to onset of event (first occurrence)
- Duration of event: that is the max duration for those events that have no interruptions during the 7 days (eg if event is on day 1, on day 3, day 4 and day 5 then duration is 3 days. Duration will be calculated considering the stop date from the AEs CRF page for those events that last beyond day 7)

The Solicited AEs will be summarized by treatment group using percentages of participants, overall and by severity (i.e. tables will include any severity, Mild, Moderate and Severe)

- Solicited AEs during 7 days after each vaccination
- Solicited AEs during 7 days after each vaccination overall (any) and by maximum severity (mild, moderate, severe)

Additionally, the following summaries will be provided for Groups 2a and 2b combined (ARCT-2303), Groups 3a and 3b combined (QIV/aQIV):

- Solicited AEs during 7 days post Day 1 vaccination
- Solicited AEs during 7 days post Day 1 vaccination by reaction
- Solicited AEs during 7 days post Day 1 vaccination by grade

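### SAP 7.1 gives no by-site display of Day 1 local reactions and no rule for combining the two arms, so the group rates cannot show whether co-administration changes either vaccine's local reactogenicity.

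*SAP*

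**What the plan says.** **Collection.** Protocol 8.12.3 fixes the Day 1 sites. ARCT-2303 always goes into the left arm and the influenza vaccine always into the right. Group 1 gets both; in Groups 2 and 3, saline takes the place of the vaccine that is not given. For Group 2, for example, the text reads "Groups 2a and 2b will receive: ARCT-2303 on the left arm and placebo on the right arm".

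On recording, the same section states that the "participant will be instructed to record local reactogenicity for both arms separately", and the protocol synopsis repeats the instruction. SAP 5.6 shows that injection location is also recorded.

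**Analysis.** SAP 3.1 presents safety summaries by treatment group and visit. SAP 7.1 follows it: "Information on Solicited Adverse Events will be summarized descriptively by treatment group, as described in section 3.1". The counts are percentages of participants, overall and by severity, with onset and duration summarized by group. SAP 7.1 also adds Day 1 tables for two pooled columns, 2a+2b labelled ARCT-2303 and 3a+3b labelled QIV/aQIV, broken down by reaction and grade. None of these tables is by injection site.

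The only rule in SAP 7.1 for reports from two arms concerns Day 29, when a single injection is given. Protocol Table 10 tabulates by study arm, but Protocol Table 6 uses that term for Groups 1a to 3b, so it does not supply a by-site display. SAP 3.1 and 10.1 exclude individual listings from the first final analysis, which carries the reactogenicity results.

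**The concern.** The secondary safety objective covers reactogenicity of the study vaccines both co-administered and alone, and Protocol 2.1 says the study is designed to ensure that neither vaccine interferes with the safety of the other. For local reactions, that question is answered by comparing the same product's site across groups: the ARCT-2303 site in Group 1 against Group 2, and the influenza site in Group 1 against Group 3. The design fixes the sites and the diary records them, so the data for these contrasts exist.

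A single participant-level rate per group does not use that information. If either arm counts, Group 1 is scored on two active sites, and Groups 2 and 3 on one active and one saline site. A higher Group 1 rate is then expected even if neither vaccine affects the other at its site. Time to first onset, maximum grade and duration raise the same question of which site is being described. In the pooled columns, and in the safety subgroup tables of SAP 3.9 that use the same pooling, saline-site reactions can appear under a vaccine label.

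**Working it through.** The documents give no figure for this point, so there is nothing to reproduce. The following is an illustration of size.

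**Inputs**
- ARCT-2303 site rate 52.4% and saline site rate 15.3%. These are the solicited local reaction rates for ARCT-154 and placebo in Protocol 2.1.2 (study ARCT-154-01). They come from a sister vaccine over two doses and are used here as single-visit site rates.
- Influenza-site rate: not in the documents; assumed 20% to 50%.
- No interaction: each product's site rate is the same in every group.
- Counting rule: either arm. This is inferred, because the SAP does not state it.

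**Formula.** For independent arms with site rates pL and pR, the either-arm rate is 1 - (1 - pL)(1 - pR).
- Group 2: 1 - (0.476)(0.847) = 59.7%, which is 7.3 points above the vaccine site's 52.4%.
- Group 1, influenza site 20%: 1 - (0.476)(0.80) = 61.9%. At 30%: 1 - (0.476)(0.70) = 66.7%. At 50%: 1 - (0.476)(0.50) = 76.2%.
- Group 3, influenza site 30%: 1 - (0.70)(0.847) = 40.7%.

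Two sites on one person are unlikely to be independent, so correlation was added through a bivariate-normal latent model. At perfect correlation the either-arm rate is the larger of the two site rates. Differences below are from unrounded values.

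| Influenza site | Correlation | Group 1 | Group 2 | Group 3 | 1 minus 2 | 1 minus 3 |
|---|---|---|---|---|---|---|
| 20% | 0 | 61.9% | 59.7% | 32.2% | +2.2 | +29.7 |
| 20% | 0.7 | 54.2% | 53.5% | 25.9% | +0.8 | +28.3 |
| 30% | 0 | 66.7% | 59.7% | 40.7% | +7.0 | +26.0 |
| 30% | 0.5 | 59.6% | 55.1% | 36.0% | +4.5 | +23.6 |
| 50% | 0 | 76.2% | 59.7% | 57.7% | +16.5 | +18.5 |
| 50% | 0.7 | 63.9% | 53.5% | 51.2% | +10.4 | +12.7 |

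Over influenza rates of 20-50% and correlations of 0-0.7, Group 1 minus Group 2 runs from +0.8 to +16.5 points, and Group 1 minus Group 3 from +12.7 to +29.7.

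**Saline lift in Group 2.** It is +7.3 points with independent arms, +2.7 at correlation 0.5, +1.1 at 0.7 and 0 at perfect correlation. If the saline site rate were 5%, the lift would be at most +2.4.

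**Limiting case.** At perfect correlation, Group 1 minus Group 2 is also 0 when the influenza rate does not exceed the ARCT-2303 rate. Group 1 minus Group 3 is not: with a 30% influenza site it is 52.4 - 30.0 = 22.4 points.

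**By site, same assumptions.** The ARCT-2303 site is 52.4% in Groups 1 and 2 (difference 0), and the influenza site is equal in Groups 1 and 3 (difference 0). The by-site display returns the no-interaction truth at any correlation.

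**The case against.** The strongest reply is that the participant-level rate is the protocol's own summary. Protocol Table 4 defines the estimand as a proportion of participants with solicited events, and Table 10 follows it. Group 1 being higher because two vaccines were given is a real burden to the participant, and describing it is a legitimate part of the safety objective. This stands: the by-site tables supplement that rate and do not replace it.

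Second, the SAP never writes an either-arm rule. A merging rule appears only for Day 29, when reports from both arms are anomalous. Its absence for Day 1 is compatible with an intention to keep the arms apart, and table shells, which are not in these documents, might do so. This stands too. A reader might infer that the SAP prescribes a wrong analysis under which co-administration is bound to look worse; the text supports only an unstated rule and an unspecified display.

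Third, a reader might infer that the pooled tables also create a false co-administration excess. They contain no co-administration group, so they cannot. The issue there is limited to possible saline-site reactions under a vaccine label.

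Fourth, the sizes rest on borrowed and assumed rates and on the correlation, and by-site tables could be produced later without loss of data. That limits the urgency. It does not remove the gap in the specified outputs, particularly for a first report that has no listings.

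**Conclusion.** The point holds as a gap in specification. Day 1 local reactions are collected by arm at fixed product sites, but the plan commits to no by-site display and does not say how two arms become one participant-level result. On the plain reading, the group rates describe total local burden and cannot show whether co-administration alters either vaccine's local reactogenicity.

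With no interaction, Group 1 would exceed Group 2 by about 1 to 17 points, and saline-site reactions would lift Group 2 by about 1 to 7 points. Both ranges depend on the either-arm reading, the two-dose sister-vaccine rates, the assumed 20-50% influenza-site rate and correlation of 0-0.7. Both quantities reach zero at perfect correlation, the Group 1 excess over Group 2 doing so when the influenza rate is no higher than the ARCT-2303 rate. They are illustrations and not forecasts.

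Protocol 10.1 makes safety descriptive. No tested hypothesis, immunogenicity objective or systemic AE table is affected. The change is worth making because it is cheap and bears directly on a stated objective.

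**What to change.** In SAP 7.1:
- State how Day 1 reports from the two arms are combined for any participant-level local-reaction rate.
- Add Day 1 local-reaction tables (any, by reaction, maximum grade, onset, duration) by injection site and product, within each age cohort. Set the ARCT-2303 site in Group 1 beside Group 2 and the influenza site in Group 1 beside Group 3, with the saline sites shown separately.
- In the pooled tables, use ARCT-2303-site data for 2a+2b and influenza-site data for 3a+3b.
- Keep the either-arm participant rate, labelled as such, since it matches the protocol's estimand.

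The cost is SAP wording and a few more tables. The by-arm diary entries and injection locations are already collected.

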**Table 1 Severity Grading for Solicited Local Reactions and Systemic Adverse Events**

	Mild	Moderate	Severe
Pain	No interference with daily activities	Interferes with daily activities	Prevents daily activity
Erythema	25-50 mm	51-100 mm	> 100 mm
Swelling	25-50 mm	51-100 mm	> 100 mm
Fatigue	No interference with daily activities	Interferes with daily activities	Prevents daily activity
Headache	No interference with daily activities	Interferes with daily activities	Prevents daily activity
Myalgia	No interference with daily activities	Interferes with daily activities	Prevents daily activity
Arthralgia	No interference with daily activities	Interferes with daily activities	Prevents daily activity
Nausea	No interference with daily activities	Interferes with daily activities	Prevents daily activity
Dizziness	No interference with daily activities	Interferes with daily activities	Prevents daily activity
Chills	No interference with daily activities	Interferes with daily activities	Prevents daily activity
Fever (°C)	38.0-38.4	38.5-38.9	≥39.0

Note: Based on Food and Drug Administration (FDA) Guidance Document: Toxicity Grading Scale for Healthy Adult and Adolescent Volunteers Enrolled in Preventive Vaccine Clinical Trials.

The following parameters will be summarized by treatment group using descriptive statistics:

- Time to onset of event (first occurrence)
- Duration of event: that is the max duration for those events that have no interruptions during the 7 days (eg if event is on day 1, on day 3, day 4 and day 5 then duration is 3 days. Duration will be calculated considering the stop date from the AEs CRF page for those events that last beyond day 7)

The Solicited AEs will be summarized by treatment group using percentages of participants, overall and by severity (i.e. tables will include any severity, Mild, Moderate and Severe)

- Solicited AEs during 7 days after each vaccination
- Solicited AEs during 7 days after each vaccination overall (any) and by maximum severity (mild, moderate, severe)

Additionally, the following summaries will be provided for Groups 2a and 2b combined (ARCT-2303), Groups 3a and 3b combined (QIV/aQIV):

- Solicited AEs during 7 days post Day 1 vaccination
- Solicited AEs during 7 days post Day 1 vaccination by reaction
- Solicited AEs during 7 days post Day 1 vaccination by grade
- Solicited AEs during 7 days post Day 1 vaccination by reaction and grade

Implausible data values reported by the study participants in the electronic diary will be excluded from analysis (rule established before any planned analysis).

Implausible values are defined as:

- A measurement >200 mm for any local injection site erythema and swelling.
- A body temperature of <33°C and >43°C.

For the reported solicited local AEs from both arms after Day 29 vaccination: If a subject reports symptoms from different arms on different days, the symptoms should be combined; If a subject reports symptoms from both arms on the same day, only the data from the left arm will be analyzed and reported in the summary tables, and all solicited local AEs (from both left and right arms) will be presented in the reactogenicity listings (rule established before any planned analysis).

The following will be summarized by treatment groups:

- Use of antipyretics and analgesics will be summarized by frequency and percentage of participants reporting use.
- Body temperature will be summarized by 0.5°C increments from 38.0°C up to  $\geq 40.0^{\circ}$  C.

